6.5.5.2 Reactions to Dosing at Home

With the occurrence of symptoms of an acute reaction to IP after home-dosing, or any acute allergic reaction, parents/guardians are instructed to call the study site. The Investigator must then determine whether or not the dose was tolerated (Section 6.5.3). Because of the reduced reliability inherent in the second-hand reporting of symptoms, Investigators are strongly encouraged to have subjects return to the clinic to undergo dosing under direct observation whenever acute allergic symptoms associated with dosing are reported.

When symptoms of a dose-related allergic reaction are reported during the course of daily home-dosing, the Investigator must assess the severity of the reaction and whether the dose associated with the reaction was tolerated. The appropriate intervention will depend on the type and severity of symptoms (Figure 2).

In general, moderate or severe symptoms will be considered clinically significant, and any dose eliciting such symptoms *assessed as not tolerated*; however, mild symptoms may also be considered clinically significant (eg, if affecting multiple organ systems, increasing in intensity, occurring with increasing frequency, or affecting a larger area over time) and *assessed as not tolerated*. Whenever there is question as to the clinical significance of mild signs or symptoms, the Investigator should have the subject return to the CRC for observed dosing under medical supervision.

For home-doses *assessed as not tolerated* on the basis of acute dose-related symptoms, the same procedures described in Section 6.5.5, above, for adjusting up-dosing should be followed.

[figure not shown]
The recurrence of mild symptoms over the course of several days of home-dosing should suggest that the dose level is not tolerated, even if each individual occurrence of symptoms could be assessed as tolerated on the basis of the criteria listed above. In this circumstance, Investigator judgment will be required to determine the best course of action with the possible actions being the following:

- Continue with daily home-dosing at the current dose level
- Continue the same daily dose for the rest of the 2-week interval, with the dose split into 2 fractional doses given 8 to 12 hours apart (the 2 fractional doses need not be equal)
- Return to the CRC for repeat dosing at the current dose level under direct observation to confirm whether or not the dose level is tolerated

- Return to the CRC for dosing of a previously tolerated dose level, either a 1- or 2-step reduction (per Investigator judgment, based on severity of reaction). Dosing must be at a dose level listed in [Table 2](#).
- Institute the 4-week hiatus from dosing, with resumption of dosing at the 3 mg/d dose level, as permitted for recurrent GI symptoms occurring at or before the 20 mg dose level
- Discontinuation of dosing, with subsequent completion of an Early Discontinuation Visit

Any subject who discontinues up-dosing due to severe or repeated allergic reactions to IP should have their blood drawn for the assessment of peanut-specific immunoglobulin and CBC at, or as nearly as possible to, the time of the last dose but no later than at their Early Discontinuation Visit (Section [6.3.6](#)). Additional assessments are to be performed per Early Discontinuation Visit schedule.

Figure 2: Schematic for Up-dosing Period Dose Adjustment

Dose Adjustment in Response to Adverse Events

At the Investigator discretion, temporary dose reductions ranging from a 1-step decrement (ie, to the previous dose) to approximately half of the current dose level (to the nearest feasible available whole dose listed in [Table 2](#)) can be instituted as part of the treatment regimen for an inter-current AE. Dosing below 3 mg/day is not allowed. Also, if a pattern of decreased tolerability of IP during menses is discerned, then a temporary dose reduction can be instituted during this time. Temporary dose reductions for inter-current AEs may be instituted as follows:

- For dose reductions of \leq 4 consecutive days, whether dose re-escalation is to occur at home or in the CRC is at the Investigator's discretion. If the reduction in dose is maintained for \leq 4 consecutive days, then the pre-reduction dose level may be resumed, with the biweekly escalation schedule kept unaltered.
- If a reduction in dose is maintained for 5 to 7 consecutive days, then the subject is to return to the CRC to undergo dosing under medical supervision. At the Investigator's discretion, the pre-reduction dose level may be resumed or dosing may continue at the reduced dose level. The biweekly escalation should be reset so that the subject receives \geq 2 consecutive weeks of treatment at the dose level assigned (either the reduced or the pre-reduction dose level).
- If a reduction in dose is maintained for 8 to 14 consecutive days, then the next escalation attempted must be conducted in the clinic, and it should only be to 1 dose level above the reduced dose. If the escalation is successful, the subject should continue home-dosing for a minimum of 2 weeks, with his or her biweekly escalation schedule reset as necessary.

Doses of IP may also be withheld at the Investigator's discretion, in response to an inter-current AE. Doses withheld as part of the treatment for an AE constitute a special category of missed peanut OIT doses ([Section 6.6](#)).

6.5.6 Treatment for Reactions During the Up-dosing Period: Pharmacological and Supportive Treatments

Treatment of acute reactions should be with either an antihistamine and/or epinephrine, along with IV fluids, a beta-agonist (eg, albuterol, by inhaler or nebulizer), oxygen, and/or corticosteroids, as indicated.

Many mild acute allergic reactions can be transient and self-limiting, requiring no therapeutic intervention. Others, however, may require treatment. Generally, for mild symptoms requiring treatment, the subject should receive antihistamines.

Acute allergic reactions manifesting with moderate symptoms will generally require therapeutic intervention, although some, even moderate, symptoms may on rare occasion be so transient as to require no specific treatment. Generally, for moderate symptoms requiring treatment, the subjects should receive antihistamines and/or epinephrine, as indicated. If there is uncertainty as to the severity of the reaction, administering epinephrine would be considered the most appropriate course of action.

Generally, severe symptoms will require treatment with epinephrine at a minimum. If severe symptoms that qualify as Stage 3 anaphylaxis (defined in [Appendix 4](#)) occur at any time, dosing with IP will stop and the subject will be discontinued from the study as an escalation failure non-responder.

Antihistamines

If a subject receives antihistamines only, the dose escalation can be continued. If epinephrine is administered, then a different course of action is to be taken.

Epinephrine - General

Any reaction to IP (in clinic or at home) that requires more than 2 doses of epinephrine will halt all further dosing of IP for the individual. The subject will be asked to return to the CRC 14 days following the last dose of IP to undergo an Early Discontinuation Visit (Section [6.3.6](#)).

Epinephrine - Clinic

If a single administration of epinephrine is required during, or after, a dose escalation in the clinic, no further dosing of IP is to occur at that visit. The next dose of IP is to be reduced by 2 dose levels and administered in the CRC, but biweekly dose escalation should continue.

If a single administration of epinephrine is required a second consecutive time during, or after, 1 escalation attempt, the dose should be reduced by 2 dose levels, and the subject continued at that dose level for 6 to 8 weeks. After 6 to 8 weeks at the reduced dose, an escalation attempt may be tried in clinic.

If a single administration of epinephrine is required a third consecutive time during an escalation attempt, no further dosing should be attempted. Dosing in these subjects will be discontinued. They will be asked to return to the CRC 14 days following their last dose of IP to undergo an Early Discontinuation Visit (Section [6.3.6](#)).

Epinephrine - Home

If a single administration of epinephrine is given during dosing at home, this epinephrine use is not counted as one of the uses described above, unless severe anaphylaxis is assessed to have occurred at home. Administration of epinephrine outside of the clinic should be followed immediately by the subject being taken to the nearest emergency department. The subject should return to clinic for an observed dose under medical supervision prior to resuming any dosing at home.

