6.5.5 Treatment for Reactions During the Up-dosing Period: Dose Adjustment

If a dose or dose level is assessed *as not tolerated*, the action taken will depend on the type and severity of the dose-related reaction and the Investigator's clinical judgment. Dosing must be at a dose level listed in [Table 2](#); dosing below 3 mg/day is not allowed. The following possible actions are at the Investigator's disposal and are considered in greater detail in subsequent sections (Section 6.5.5.1, Section 6.5.5.2, and [Figure 2](#)):

- Dosing the subject under medical supervision in the CRC – this is encouraged whenever there is question as to the tolerability of a dose level. It may be performed at the current dose level or at a reduced dose level, if there is already a high index of suspicion that the current dose level has not been tolerated.
- Holding dose level at current level for an additional 1 to 2 weeks before attempting dose escalation – this may be done at the discretion of the Investigator if there is concern that the current dose level has not been sufficiently well tolerated to attempt up-doing to the next dose level.
- Reducing dose by 1 or 2 dose levels and maintaining the reduced dose level for ≥ 2 - to 4-week period before attempting dose re-escalation – Generally, this should be the

action taken when a dose that has been observed in the CRC is assessed as not tolerated, if a dose elicits moderate or severe reactions that require no more than a single dose of epinephrine for treatment, or if the Investigator is convinced of the intolerability of the current dose level. In short, it should be considered the default action whenever a dose or dose level is assessed *as not tolerated*.

- Reducing dose level for less than the usual 2-week period – this may be instituted as treatment for an inter-current AE, to aid the Investigator in determining if a dose level is or is not tolerated, or if a pattern of decreased IP tolerability during menses is discerned. The level of the reduction in dose, ranging from a 1-step reduction to a 50% reduction will be at the Investigator's discretion, based on clinical judgment. The manner in which dose escalation may resume will depend on the level and the duration of the dose reduction.

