- Temporarily withholding IP dosing – this may be instituted as treatment for an inter-current AE or to aid the Investigator in determining if a dose level is or is not tolerated, but the duration of withholding IP may not exceed 14 consecutive days, or the subject will be discontinued from the study. The manner in which dosing may resume after withholding dosing of IP depends on the duration for which dosing was withheld.
- Reducing dose by 2 dose levels and maintaining the reduced dose level for at least 6 weeks – continuing dosing at a reduced dose level for at least 6 weeks prior to attempting re-escalation is mandatory if 2 doses of epinephrine are given to treat a single AE. In this case, discussion with the Medical Monitor is mandatory at 6 weeks, prior to the next up-dosing, to determine if dose escalation is warranted.
- Stopping dosing and discontinuing the subject early from the study – this is an option that the subject may elect at any time and for any reason. The Investigator must discontinue the subject from further dosing and continuation in the trial under circumstances that could jeopardize the health of the subject or the integrity of the trial.

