6.5.5.1 Reactions to In-clinic Dosing

If symptoms arise in the clinic after up-dosing, the Investigator is to determine whether or not the dose was tolerated (Section 6.5.3). The process algorithm for continued dosing after dose-related symptoms occur is described below and shown in [Figure 2](#).

If a subject has a dose escalation in the CRC without symptoms, the action should be to continue, per protocol, with daily home-dosing at the tolerated dose level and return to the CRC for the next scheduled dose escalation visit 2 weeks later.

If the subject experiences only *oral/pharyngeal pruritus* following the administration of the first dose at a new dose level, the dose will generally be *assessed as tolerated*, and the same dose can be repeated the next day at home and continued throughout the 2-week home-dosing interval, unless other symptoms begin to develop.

If other *mild symptoms* occur with the first dose at a new dose level and the dose is *assessed as not tolerated*, the action taken should be to have the subject return to the CRC the next day for dosing at the last tolerated dose (ie, a 1-step dose reduction) under medical supervision (if the subject is unable to return to the CRC on the day specified, the Investigator may initiate an

approximate 1 dose-level reduction at home, with the subject coming to the CRC at the earliest date possible). Dosing below 3 mg/day is not allowed. If the reduced dose is *assessed as tolerated*, the subject is to continue on that daily home dose for the ensuing 2 weeks. (See Section 6.5.5.2 for actions to be taken in the event that symptoms develop during home-dosing.) If the reduced dose is again *assessed as not tolerated*, the subject is to return to the CRC the next day for supervised dosing at a 1- or 2-step reduction in dose (per Investigator judgment, based on severity of reaction). If this further reduced dose is *assessed as tolerated*, the subject will continue at that dose level for daily home-dosing over the ensuing 2 weeks. If, however, the reduced dose is *assessed as not tolerated*, the subject is to be considered an escalation failure non-responder and will be asked to return to the CRC 14 days following their last dose of IP to undergo an Early Discontinuation Visit (Section 6.3.6).

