If *moderate symptoms* occur with the first dose at a new dose level, except for rare instances, the dose will be *assessed as not tolerated*. The action taken should be to have the subject return to the CRC the next day for dosing at the last tolerated dose under medical supervision. Dosing below 3 mg/day is not allowed. If this reduced dose elicits no allergic symptoms (ie, is well tolerated), the subject will continue on that daily home dose level for an additional 2 weeks. If the subject experiences mild symptoms at the reduced dose, the procedures for responding to a dose with mild symptoms should be followed (see above and Figure 2). If the subject experiences moderate symptoms at the reduced dose level, the subject should return to the CRC the next day and receive a further 1- or 2-step dose reduction (per Investigator judgment). If this reduced dose is well tolerated, it will be continued as the daily home dose for ≥ 2 weeks before re-escalation is attempted in the CRC. If the dose is not well tolerated, but elicits mild symptoms, then the treatment procedures for responding to mild symptoms should be followed (see above and Figure 2). If, however, the subject again experiences moderate symptoms at the reduced dose level, a discussion with the Medical Monitor is to ensue to reach a decision as to whether to continue the subject in the study.

In the rare instance that a dose eliciting moderate symptoms is *assessed as tolerated*, then the actions taken should be the same as for a dose with mild symptoms *assessed as tolerated*.

If *severe symptoms* occur, the action should be to treat the subject for the allergic reaction, and then, in consultation with the Medical Monitor, decide whether or not to discontinue the subject from the study. If it is determined that it is safe to allow the subject to continue in the study, the

subject should return to the CRC the next day for dosing at a 2-step reduction in dose under observation. Dosing below 3 mg/day is not allowed. If the subject tolerates the dose reduction (ie, shows no or only mild symptoms that are assessed as tolerated), then the subject is to remain at the reduced dose level for \geq 2 weeks before returning to the CRC to attempt dose re-escalation. If the subject does not tolerate the reduced dose, then the subject is to be considered an escalation failure non-responder.

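### After a first single in-clinic epinephrine dose for a mild not-tolerated or moderate up-dosing reaction, Protocol 6.5.6 and 6.5.5.1 set different next doses, and the text of 6.5.5 and 6.5.5.1 does not say which governs

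*Protocol*

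**What the plan says.** **Section 6.5.6, Epinephrine - Clinic.** After a single epinephrine administration during or after an in-clinic escalation, dosing stops for that visit. Then: "The next dose of IP is to be reduced by 2 dose levels and administered in the CRC, but biweekly dose escalation should continue". No severity condition is attached. Just before this, under Antihistamines, the same section says: "If epinephrine is administered, then a different course of action is to be taken".

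**Section 6.5.5.1, mild symptoms, dose not tolerated.** The child comes back on the following day, and the step is "dosing at the last tolerated dose (ie, a 1-step dose reduction) under medical supervision". Where a return that day is not possible, the investigator may start an "approximate 1 dose-level reduction at home, with the subject coming to the CRC at the earliest date possible".

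**Section 6.5.5.1, moderate symptoms.** Such a dose nearly always counts as a failure of tolerability, and the response is: "The action taken should be to have the subject return to the CRC the next day for dosing at the last tolerated dose". Staff supervise that visit.

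**Section 6.5.5, list of actions.** One bullet, described as the default for a dose that is not tolerated, opens "Reducing dose by 1 or 2 dose levels and maintaining the reduced dose level for" at least 2 to 4 weeks. Among the situations it covers is "if a dose elicits moderate or severe reactions that require no more than a single dose of epinephrine for treatment". A separate bullet sets a two-level reduction held for at least 6 weeks, which "is mandatory if 2 doses of epinephrine are given to treat a single AE".

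**Section 6.3.3.** For the delay in escalation after epinephrine, the text refers to Section 5.8.

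**The concern.** One clinical event can fall under two rules with different next doses. Section 6.5.5.1 looks only at severity and tolerability; the 6.5.6 rule looks only at whether epinephrine was given. Neither 6.5.5 nor 6.5.5.1 refers to 6.5.6 or makes an exception for reactions treated with epinephrine.

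The overlap is foreseen by the protocol itself. Section 6.5.2 lists the need for one epinephrine dose as a reason to call a mild reaction not tolerated. Section 6.5.6 allows antihistamines, epinephrine or both for moderate symptoms, and prefers epinephrine when severity is uncertain.

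At stake is the allergen dose given to a child who has just needed epinephrine. A site working from 6.5.5.1 can give a higher dose than 6.5.6 sets and, in some mild cases, can give it at home where 6.5.6 requires the CRC.

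**Working it through.** The plan states no figure for this point, so there is none to reproduce. The check compares the texts and then applies both rules to the dose ladder.

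**Step 1. The rules by severity, after one epinephrine dose for an in-clinic up-dosing reaction**

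| Reaction | 6.5.5.1 | 6.5.6 | Same? |
|---|---|---|---|
| Mild, not tolerated | 1 step lower (stated); CRC, or home if unable to return | 2 levels lower; CRC | No |
| Moderate | Last tolerated dose; CRC | 2 levels lower; CRC | No, by inference |
| Severe, continuing in study | 2 steps lower; CRC | 2 levels lower; CRC | Yes |

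For moderate reactions, one level lower is an inference. At the first dose of a new level, the last tolerated dose is normally the level just left. Only the mild paragraph equates the two in words.

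**Step 2. The dose difference**

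Inputs: the Table 2 levels (3, 6, 12, 20, 40, 80, 120, 160, 200, 240 and 300 mg) and the 3 mg/day floor in 6.5.5. For a reaction at level i, compare dose(i-1) with the larger of dose(i-2) and 3 mg.

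| Reaction at (mg) | 1 level lower | 2 levels lower | Ratio |
|---|---|---|---|
| 6 | 3 | 3 (floor) | 1.0 |
| 12 | 6 | 3 | 2.0 |
| 20 | 12 | 6 | 2.0 |
| 40 | 20 | 12 | 1.67 |
| 80 | 40 | 20 | 2.0 |
| 120 | 80 | 40 | 2.0 |
| 160 | 120 | 80 | 1.5 |
| 200 | 160 | 120 | 1.33 |
| 240 | 200 | 160 | 1.25 |
| 300 | 240 | 200 | 1.2 |

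The dose differs at 9 of 10 levels: twofold at four of them, and by 1.2 to 1.67 at the other five. Every dose in the two middle columns is below the dose that caused the reaction.

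**Step 3. Time to return to the failed level**

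With 2-week steps, one level lower takes 2 weeks and two levels lower takes 2 × 2 = 4 weeks, a difference of 2 weeks. At 6 mg both rules take 2 weeks.

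**Step 4. The cross-reference**

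Section 5.8 covers rescue medication and auto-injector supply and contains no delay rule. The hold of 6 to 8 weeks after a second consecutive single in-clinic administration is in 6.5.6.

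**The case against.** The best reply is that the specific rule governs the general one. Section 6.5.6 announces a different course once epinephrine is given, follows with a dedicated in-clinic rule, and words it as a requirement. Section 6.5.5.1 is general and advisory in tone. Two levels also lies within the range of one or two in 6.5.5. The Medical Monitor is available for dosing questions the protocol leaves open, and every epinephrine-associated AE must be reported within 24 hours (7.3.4.5).

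Most of this stands. It shows which rule was probably meant, and a careful site would probably go down two levels. It does not close the gap, because 6.5.5 also addresses reactions needing a single epinephrine dose and permits one level there. The reporting rule does not set the next dose.

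Four further limits stand:

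- Sections 6.5.5, 6.5.5.1 and 6.5.5.2 all send the reader to Figure 2, which was not available and may carry an epinephrine branch.
- The home case needs a mild reaction, epinephrine, and a child who cannot return. Section 6.5.6 says mild symptoms needing treatment should generally get antihistamines, so the case is uncommon.
- Section 6.3.3 points to 6.5.5 for severity-based adjustment, but in the setting of a suspected failure to tolerate the current level. That is weak evidence that sites are led away from 6.5.6.
- The one-level dose is one the child had tolerated, ordinarily for about 2 weeks, and after a moderate reaction it is supervised.

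A reader might infer that children were in fact overdosed after epinephrine, or that the safety results are distorted. The documents support neither. They give no frequency for such events and do not show how sites resolved them.

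**Conclusion.** The two rules conflict in the protocol text for mild not-tolerated and moderate in-clinic up-dosing reactions treated with a first single epinephrine administration. Section 6.5.6 is probably meant to govern, but 6.5.5 and 6.5.5.1 do not say so. The conflict does not extend to severe reactions, where the step size agrees, and at the 6 mg level the floor makes the doses equal.

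The conclusion rests on two assumptions: that the last tolerated dose after a moderate reaction is normally one level lower, and that Figure 2 does not already direct epinephrine-treated reactions to the 6.5.6 rule. Confidence is medium because of the second. The Section 5.8 cross-reference is a separate small error that stands whatever Figure 2 shows.

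Priority: a minor safety clarification.

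**What to change.** In 6.5.5 and 6.5.5.1, and in Figure 2 if it lacks this branch, add:

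*If a single dose of epinephrine was given for a mild or moderate reaction to an in-clinic up-dosing dose, the size and place of the next dose follow Section 6.5.6: 2 dose levels lower (not below 3 mg/day), given in the CRC. All other steps of 6.5.5 and 6.5.5.1 still apply, including what to do if the reduced dose is not tolerated and Medical Monitor consultation, as do the rules for repeated or multiple epinephrine doses and the stopping rules.*

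In the 6.5.5 bullet that allows one or two levels, add: *(2 levels after a single in-clinic epinephrine administration; see Section 6.5.6)*. In 6.3.3, change the Section 5.8 reference for the epinephrine delay to 6.5.6.

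The statement should replace only the size and place of the next dose. Telling sites to follow 6.5.6 instead of the whole severity-based procedure could displace the Medical Monitor consultation and the 6.5.5.1 steps for a reduced dose that also fails. Two levels is the natural choice because it satisfies both 6.5.6 and 6.5.5; one level satisfies only 6.5.5.

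Costs:

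- A short protocol amendment, with the Sponsor and IRB/EC approval and health-authority submission that Section 10.1 requires. No added patients.
- About 2 extra weeks per event at 12 mg or above for children who would otherwise have had the one-level step. The margin between the 20-week minimum and the 40-week cap is 40 - 20 = 20 weeks. If nothing else delays escalation, that covers 20/4 = 5 separate, non-consecutive events against 20/2 = 10.
- Loss of the home option in rare mild cases. The child may miss doses while waiting for the CRC visit, and Section 6.6 treats missed up-dosing doses as a risk, though it requires a dose reduction only from five missed in a row.

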Appendix 4: Criteria for Suspected Diagnosis, and Severity Grading, of Anaphylaxis

Criteria for Suspected Diagnosis

Anaphylaxis is likely when any 1 of the 3 following sets of criteria is fulfilled:

1. Acute onset of an illness (minutes to hours) with involvement of:
 - Skin/mucosal tissue (eg, *generalized* hives, itch or flush, swollen lips/tongue/uvula) *AND*
 - Airway compromise (eg, dyspnea, stridor, wheeze/ bronchospasm, hypoxia, reduced PEFR) *AND/OR*
 - Reduced BP or associated symptoms (eg, hypotonia, syncope, incontinence)
2. Two or more of the following that occur rapidly after exposure to the allergen (minutes to hours):
 - Skin/mucosal tissue (eg, *generalized* hives, itch/flush, swollen lips/tongue/uvula)
 - Airway compromise (eg, dyspnea, stridor, wheeze/bronchospasm, hypoxia, reduced PEFR)
 - Reduced BP or associated symptoms (eg, hypotonia, syncope, incontinence)
 - *Persistent* GI symptoms (eg, nausea, vomiting, crampy abdominal pain)
3. Reduced BP after exposure to the allergen (minutes to hours):
 - Infants and children: low systolic BP (age-specific) or > 30% drop in systolic BP*
 - Adults: systolic BP < 90 mm Hg or > 30% drop from their baseline

* *Low systolic BP for children is defined as < 70 mmHg from 1 month to 1 year; less than (70 mmHg + [2 x age]) from 1 to 10 years; and < 90 mmHg from age 11 to 17 years.*

Note: Isolated skin or mucosal lesions following the ingestion of a food constitute a food-induced allergic reaction.

Criteria for Anaphylaxis Severity Grading

Staging System of Severity of Anaphylaxis	
Stage	Defined by
1. Mild (skin and subcutaneous tissues, GI, and/or mild respiratory)	Flushing, urticaria, periorbital, or facial angioedema; mild dyspnea, wheeze, or upper respiratory symptoms; mild abdominal pain and/or emesis
2. Moderate (mild symptoms + features suggesting moderate respiratory, cardiovascular or GI symptoms)	Marked dysphagia, hoarseness, and/or stridor; shortness of breath, wheezing and retractions; crampy abdominal pain, recurrent vomiting, and/or diarrhea; and/or mild dizziness
3. Severe (hypoxia, hypotension, or neurological compromise)	Cyanosis or SpO ₂ ≤ 92% at any stage; hypotension; confusion; collapse; loss of consciousness; or incontinence

Criteria for diagnosis and for severity grading adapted from [Muraro et al, 2007](#), and [Muraro et al, 2014](#).

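### Protocol Section 6.5.6 is internally inconsistent on severe (Stage 3) anaphylaxis after a home dose: one rule stops dosing, while the home-epinephrine rule enters the same event in a count whose first two steps continue it

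*Protocol*

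**What the plan says.** Section 6.5.6 of the protocol covers pharmacological and supportive treatment of reactions during up-dosing. Its general text holds a stop rule. It begins "If severe symptoms that qualify as Stage 3 anaphylaxis" and, after a pointer to Appendix 4, goes on: "occur at any time, dosing with IP will stop and the subject will be discontinued from the study as an escalation failure non-responder". The rule is not limited to clinic or home, and it does not depend on earlier events.

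The section then sets rules according to the epinephrine given. Under the clinic heading, single administrations at escalation attempts are counted:

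- First use: "The next dose of IP is to be reduced by 2 dose levels and administered in the CRC, but biweekly dose escalation should continue".
- Second consecutive use: "the dose should be reduced by 2 dose levels, and the subject continued at that dose level for 6 to 8 weeks". A further escalation attempt in clinic is then allowed.
- Third consecutive use: "If a single administration of epinephrine is required a third consecutive time during an escalation attempt, no further dosing should be attempted".

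Under the home heading, a single administration during home dosing is treated differently: "this epinephrine use is not counted as one of the uses described above, unless severe anaphylaxis is assessed to have occurred at home". The child is to be taken at once to an emergency department. The paragraph ends: "The subject should return to clinic for an observed dose under medical supervision prior to resuming any dosing at home".

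Section 7.4 has anaphylactic reactions graded by the system in Appendix 4. That appendix has three stages and labels Stage 3 as severe, described as "hypoxia, hypotension, or neurological compromise".

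**The concern.** The two rules in Section 6.5.6 appear to meet in one child: a child who has Stage 3 anaphylaxis after a home dose and receives one epinephrine administration. The general text discontinues that child. The home paragraph singles out the same event, but the consequence it attaches is entry into a count that begins with dose reduction and continued dosing. A count towards a later stop has no purpose if the first such event has already ended treatment.

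Severe anaphylaxis away from the clinic is among the most serious events this paediatric safety study can produce. If sites read the section differently, children with the same reaction will differ in their further exposure to study product. They will also differ in whether they count in the secondary endpoint of premature discontinuation of dosing due to adverse events (Protocol 9.2.2, SAP 4.2).

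**Working it through.** The plan gives no figure for this event, so there is nothing to reproduce. The check applies each rule to one case: Stage 3 anaphylaxis after a home dose in up-dosing, treated with a single epinephrine administration.

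**Step 1: do both rules address the same event?** The stop rule names Stage 3 and cites Appendix 4. The home paragraph says severe anaphylaxis and cites nothing. Section 7.4 grades anaphylaxis by Appendix 4, where the severe stage is Stage 3. Section 7.7.3 and Appendix 6 also tie severe anaphylaxis to Appendix 4. The likely answer is yes.

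**Step 2: apply both rules.**

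| Home event enters the count as | General stop rule, 6.5.6 | Home paragraph read with the clinic steps, 6.5.6 |
|---|---|---|
| Use 1 | Stop, discontinue | Reduce 2 levels, escalation continues |
| Consecutive use 2 | Stop, discontinue | Reduce 2 levels, hold 6 to 8 weeks, then escalation may be tried |
| Consecutive use 3 | Stop, discontinue | Stop |

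The two columns agree only in the last row. The clinic count runs over consecutive uses at escalation attempts, and the text does not say how a home use takes its place in that sequence.

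**Step 3: let one rule control.** If the stop rule controls, the child is out at the first event and the exception for severe anaphylaxis never operates. If the home paragraph is followed, the child may continue, and its closing sentence on resuming home dosing makes no exception for severe anaphylaxis. No order of precedence is stated.

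**Step 4: does other text settle it?**

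- Sections 6.3.1 to 6.3.3 agree with the stop rule: Stage 3 anaphylaxis at any time is to be discussed with the Medical Monitor and the subject discontinued.
- Section 4.3.1 requires termination for life-threatening (CoFAR Grade 4) symptoms and for severe (Grade 3) symptoms, which also points to a stop.
- Section 6.5.5 gives dose reduction as the general action when a moderate or severe reaction needs no more than one dose of epinephrine.
- Section 6.5.5.1 leaves severe symptoms to a decision with the Medical Monitor, with a 2-step reduction if the subject continues. Section 6.5.5.2 sends intolerable home doses to the procedures of Section 6.5.5.
- Section 7.9.2, the individual stopping rules, does not list Stage 3 anaphylaxis.

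Some of this text supports a stop and some does not, so the surrounding protocol does not resolve the question.

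**Step 5: scale for the endpoint.** With full enrolment, the AR101 arm has 500 × 2/3 = 333 subjects. One child handled one way or the other changes the proportion discontinued by 1/333, or 0.3 percentage points.

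**The case against.** A reader might infer that the protocol gives two opposite orders, one to stop and one to continue. The documents do not go that far. The home paragraph is a counting rule. It does not say that being counted is the only consequence, and it does not tell a site to keep dosing after severe anaphylaxis. Its last sentence is a precondition for any return to home dosing after home epinephrine, and its ordinary case is a non-severe reaction. The stop rule, by contrast, is explicit and is repeated in Sections 6.3.1 to 6.3.3. Section 4.3.1 adds a mandatory termination that names anaphylaxis with hypotension or neurological compromise, two of the three Stage 3 features. A careful site could treat the stop rule as general and the epinephrine rules as applying to subjects still on treatment. This stands against the claim of opposite orders. It does not rescue the exception, which on that reading has no function.

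A second objection is that severe anaphylaxis in the home paragraph may mean a reaction with severe symptoms short of Stage 3. The scales do differ: stridor is a severe symptom in Section 6.5.1 but belongs to Stage 2 in Appendix 4. On that reading the exception would have a use and would not collide with the Stage 3 rule. This is possible but less likely, since Section 7.4 makes Appendix 4 the scale for anaphylaxis. It shows that the term needs defining.

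Finally, Section 6.5.5.2 refers sites to the schematic in Figure 2, which could not be read for this check. It may state a path for severe home reactions and should be compared with the text.

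**Conclusion.** The point holds as an internal inconsistency. For severe anaphylaxis at home treated with one epinephrine administration, Section 6.5.6 either conflicts with itself at the first and second counted uses or contains a clause that can never take effect. This rests on reading severe as Appendix 4 Stage 3, which the protocol supports but the home paragraph does not state.

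The number of children affected cannot be computed. A reader might take the expectation in Section 1.4.1 of severe symptoms in fewer than 1% and apply it to 333 subjects, giving about 3. That figure does not measure this event: it describes severe symptoms expected from earlier oral immunotherapy studies, not Stage 3 anaphylaxis and not reactions at home. Few children are likely to be affected. At about 0.3 percentage points per child, in an endpoint summarized descriptively with no planned hypothesis test, the statistical effect is small. The case for acting is the safety of the individual child and the same handling at every site.

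**What to change.** Reconcile the general stop rule and the home-epinephrine paragraph of Section 6.5.6 so that one stated consequence applies to severe anaphylaxis at home. In the home paragraph, define severe anaphylaxis by naming the scale intended, and make the counting sentence refer only to reactions to which the count can apply. Check Sections 6.5.5, 6.5.5.1 and 7.9.2, and Figure 2, against the result. Sections 6.3.1 to 6.3.3 already match the stop rule as it stands; they need another look only if that rule itself is changed. Which consequence is right is a clinical decision for the sponsor and is not judged here.

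The cost is a short protocol clarification or a memo to sites. No analysis in the SAP has to change.
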